# 7.5 Consent procedures

Information on the Y-Check programme (both check-up visit and research cohort) will be distributed to parents/guardians through the schools and to community members through an active communication campaign in collaboration with the Community Steering Committee and the YAG. A series of school and community meetings will be held to allow the opportunity for parents and community members to ask questions about the programme and give their feedback.

The consent procedures for younger (Y-Check 1, 10-14y) and older (Y-Check 2, 15-19y) adolescents will be different reflecting their differing information needs and level of autonomy. Consent for the check-up visit (Y-Check services) will be separate to consent for the Y-Check research cohort (additional interviews and follow-up). Consent forms for the check-up visit will include parental consent for on the spot treatment or referral to specialist services. Adolescents will be able to participate in only the check-up visit or both the check-up visit and the research cohort.

Participants and, if required, their parents/guardians, will sign a paper or electronic consent (econsent) form on an electronic tablet. Participants/Parents/guardians signing an e-consent form will also sign a paper version for their own records, which contains the contact details of the study team and the MRCZ, in case they have issues or complaints about the study or choose to withdraw in the future. The e-consent form and the paper consent form would be linked through an ID number.

For **Y-Check 1 (10-14y),** parents/guardians who would like their adolescent to receive the check-up will be asked to provide written parent/guardian consent. In the weeks before or on the day of the check-up visit, the adolescent will provide written assent. For enrolment into the research cohort, both written consent from parents/guardians and written assent from the adolescent will be required.

For Y-Check 2 (15-19y) in schools, parents/guardians who would like their adolescent to receive the check-up will be asked to provide written parent/guardian consent. In the weeks before on the day of the check-up visit, the adolescent will provide written assent. For enrolment into the research cohort, both written consent from parents/guardians and written assent from the adolescent will be required. Emancipated minors (i.e. participants who are married, have children or are the main care-givers for their younger siblings) who are enrolled in school are also required to provide guardian consent and Y-Check will work with the school to identify the minor's guardian.

For **Y-Check 2** (**16-19y**) at community hubs, adolescents in the target age ranges who would like to receive the check-up will provide verbal consent on the day of the check-up visit. For enrolment into the research cohort, adolescents will provide written consent.

Adolescents will be asked to provide the contact details of an adult (18+y) whom they want us to contact if the need arises. This 'trusted adult' could be a parent or another adult who they can confide in.

During registration at the community hubs, the research team member will explain the purpose of the trusted adult to the adolescent (16-19 years) and will ask the adolescent to nominate an adult. In many cases, the trusted adult is likely to be their parent, guardian or another adult relative. When necessary, the identity of the nominated trusted adult will be verified by the research team through a phone call or in-person visit prior to the sharing of any confidential information. If the research team are concerned that the nominated trusted adult is not someone who has an interest in the adolescent's

well-being, then they will discuss again with the adolescent and make further attempts to identify an appropriate trusted adult.

Guidelines stipulate that minors defined as those aged under 18 years should have parental consent. However, in this study we request a waiver of the need for consent from a parent/guardian for those aged 16-17 years who are receiving Y-Check services at the community hubs. Following a review of existing practices within African settings and consultation with our independent scientific advisory committee, the consensus is that a waiver for consent is acceptable if the following conditions are met:

- 1. Research cannot be practically or adequately conducted without a waiver: The main concern in this study is that participants will not be able to be open about their concerns if they worry that their guardians will ask questions and will sanction them for being open. This is a particular concern in relation to sexual and reproductive health services and HIV testing and care. Experts working in the area have found that the very participants whose guardians are likely to refuse consent for them to participate are the very ones who face the most barriers to accessing services. We therefore believe that the requirement for consent will jeopardise meeting the aims of this work
- 2. Risks are minimal, and rights and welfare are not affected: We will have appropriate support services in place for participants and encourage adolescents to involve their 'trusted adult' in any health or well-being discussions or decisions.
- 3. Protection of privacy and confidentiality: Interviews will take place in a private location. All information will be maintained strictly confidentially in password-controlled databases with all identifiers stripped. Participants will be reassured that their information will not be disclosed unless holding back the information will result in harm to the participant.

A guardian will be defined as someone who is over the age of 18 years who is responsible for the daily care, welfare and management of the rights of a minor (someone aged <16 years). The guardian does not necessarily have to be related to the child. If the biological parent is alive but absent (not providing daily care for the child), the individual responsible for the daily welfare of the child will be eligible to give consent. However, the guardian will be encouraged to contact the biological parent (if possible) for consent. Emancipated minors i.e. participants who are married, have children or are the main caregivers for their younger siblings will be able to give consent independently for participation in the study. No participants will be interviewed without their informed consent. All interviews will be conducted in private and not in the presence of the parent/guardian.

Information will be provided about the study, its objectives and procedures, possible risks and procedures to maintain confidentiality. Participants and their parents/guardians will be able to ask any questions they may have. Contact details of the study team will be shared with participants in case they may have questions at a later stage. All participants will be reminded that participation is entirely voluntary and will be told that they can leave the discussion or stop the interview at any time.

The check-up consent forms and research cohort consent forms to be used are attached to this protocol. The research cohort consent forms follow the template required by the Medical Research Council of Zimbabwe, and have been translated into Shona. Written consent for participation in the research cohort will be obtained from all participants, except where a telephone interview has been requested. In these cases, the interviewer will conduct the informed consent procedure verbally, and sign the form on the respondent's behalf.

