• School recruitment (Y-Check 1 (10-14y) & Y-Check 2 (15-19y)): All students in the Y-Check target classes/forms will be eligible to participate if their parent/guardian has signed a consent form and the student has provided written assent.

• Community recruitment (Y-Check 2 (16-19y)): Participants receiving Y-Check 2 services in the community will provide their own verbal consent. Parent/guardian consent will not be required for adolescents receiving services in the community, but participants will be encouraged to share information and results with their parents/guardians or another trusted adult.

Parents/guardians/students can choose to participate in the full screening visit or part of the screening visit e.g. the pre-consultation questionnaire and nurse review only.

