#### HIV Testing and Counselling (Y-Check 2 in the community hubs only)

All participants will be offered standard provider-initiated HIV testing and counselling (PITC) using national guidelines. Clients will be offered a self-test for HIV on-site using an oral mucosal test (OMT). The staff member will provide a demonstration on the use of the OMT. All positive HIV test results will require a second confirmatory test with a blood-based rapid diagnostic test (RDT). Discordant or

inconclusive results will be further evaluated according to national guidelines. For 16-19 year olds who test positive, the counsellor/nurse will suggest that the adolescents' trusted adult be contacted so that they can join the discussion of the results and next steps. The study team will facilitate referral of those who test positive to a local health facility to register for HIV care. HIV+ adolescents will be encouraged to join adherence support groups run by local NGOs/CBOs. If HIV positive and sexually active, adolescents will be asked to refer their partners to government health clinics for HIV testing.

Sexual and reproductive health (Y-Check 2 in the community hubs only)

- All participants will be offered male condoms regardless of reported levels of risk behaviour.
  Those reporting high risk sexual behaviour (sexual intercourse without a condom, multiple sexual partners) in the pre-consultation questionnaire will be offered risk-reduction counselling.
- HIV pre-exposure prophylaxis (PrEP), which confers significant protection against HIV acquisition, is being rolled-out in Zimbabwe for populations at high risk of HIV acquisition including men who have sex with men and girls aged 15-24 years who report high risk sexual behaviours. Participants who report high risk sexual behaviour and who test negative for HIV will be referred to a local health facility to assess their eligibility to receive PrEP according to national guidelines.

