# 7.6 Information sharing and disclosure

The protocol for sharing the results of the screening tests will vary according to the perceived seriousness of the condition and the age of the participant. The conditions that will be considered more or less serious or seriously stigmatized will be decided in collaboration with adolescents and stakeholders during Phase 1. More serious or seriously stigmatised conditions may include HIV, drug use, alcohol abuse, experiencing violence, suspected epilepsy, and serious musculoskeletal disorders Less serious or seriously stigmatised conditions may include anaemia, overweight, underweight, prehypertension, hypertension, myopia or a hearing disorder.

If the adolescent is diagnosed with a condition that is considered to be more serious and/or more seriously stigmatized, the adolescent's trusted adult (Y-Check 2 community hub) or the parent/guardian (Y-Check 1 and Y-Check 2 school-recruited) will be sent a message as soon as possible indicating that they should make an appointment with the Y-Check nurse/counsellor to discuss the adolescent's health. The nurse or counsellor would then meet with the adolescent and the adult/parent(s) together and would explain the condition or suspected condition and what is being recommended. They will ask for the adult/parent's support to manage the condition and answer any questions and give advice/support as needed. If the adult/parent does not take up the offer of an appointment, the study team will consult with the adolescent, and school, health or social care staff before deciding on next steps. Potential action would include contacting the parent/guardian by phone or through a home visit, and in emergency situations referring the young person to health/social services without the support of the parent/guardian.

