If the adolescent is diagnosed with a condition that is considered to be less serious and/or less seriously stigmatized, the trusted adult (Y-Check 2 community hub) or the parent/guardian (Y-Check 1 and Y-Check 2 school-recruited) will be sent a letter indicating the diagnosis and the recommended treatment/action. Trusted adults or parents/guardians will be encouraged to support their adolescent through their treatment/care. The letter will also offer a way for the adult/parent to get an appointment with their adolescent so that they can ask any questions and receive advice/support as needed. If the adolescent needs their adult to accompany them to a referral appointment, then the Y-Check team would attempt to contact the adult by telephone or through a home visit. Otherwise, there will be no follow-up if the adult/parent does not take up the offer of an appointment.

If the adolescent is generally well then the adolescent will receive a one-page summary telling them what has been checked for and that nothing serious has been found. They will be encouraged to continue good health-related behaviours. They will be told about health and well-being services available at the school, the health facility and in the community. For Y-Check 1 and Y-Check 2 (school-recruited), the letter will be sent from the school to the parents. For Y-Check 2 (community-hub), the adolescent will receive the letter and will be encouraged to share with their trusted adult(s).

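### The confidentiality assurance supporting the 16-17 year consent waiver at the hubs is contradicted by Section 7.6, which sends a message or diagnosis letter to the trusted adult with no harm test or agreement step

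*Protocol*

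**What the plan says.** In Section 7.5 of the protocol, "we request a waiver of the need for consent from a parent/guardian for those aged 16-17 years" who receive services at the community hubs. The section adds that "the consensus is that a waiver for consent is acceptable if the following conditions are met" and lists three. The third, on privacy, ends: "Participants will be reassured that their information will not be disclosed unless holding back the information will result in harm to the participant".

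Section 7.6 sets out who is told about results, and names the hub group in both branches. For a condition classed as more serious or stigmatised, the trusted adult "will be sent a message as soon as possible indicating that they should make an appointment with the Y-Check nurse/counsellor". For a less serious condition, "the trusted adult (Y-Check 2 community hub) or the parent/guardian (Y-Check 1 and Y-Check 2 school-recruited) will be sent a letter indicating the diagnosis" together with the recommended action.

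Other sections describe sharing differently. Section 3.7, on community recruitment, says "participants will be encouraged to share information and results with their parents/guardians or another trusted adult". In the HIV testing text of Section 3.7.2, after a positive result staff only suggest that the "trusted adult be contacted so that they can join the discussion of the results and next steps".

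**The concern.** The assurance and the procedure apply to the same adolescents and cannot both be carried out as written. Staff who give the assurance and then follow Section 7.6 will send information in cases where no harm from silence has been considered and no agreement sought.

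Three features of the plan make this more than a drafting slip. The 16-17 year olds are minors taking part without parental consent. Consent to the check-up at the hubs is verbal, so what staff say carries the weight. HIV and STI testing are offered only at the hubs, so some of the most sensitive results arise where the assurance is given. Section 7.4 itself lists breach of confidentiality, and rejection or discrimination by friends and family, among the risks.

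**Working it through.** No arithmetic applies. The check sets the texts side by side.

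1. **Scope of the assurance.** Condition 3 opens with the privacy of interviews, so it could be read as covering research interviews only. But the waiver concerns adolescents receiving check-up services, and the sentence on disclosure refers to participants' information without limit. It therefore reaches screening results.

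2. **The Section 7.6 rule for the same group.**
   - *More serious branch* (examples include HIV, drug use and experience of violence). Trigger: a diagnosis. Harm test: none stated. Agreement step: none stated. The message asks the adult to book an appointment about the adolescent's health, and the condition is explained there with the adolescent present.
   - *Less serious branch* (examples include anaemia, overweight and myopia). Trigger: a diagnosis. Harm test: none stated. Agreement step: none stated. The letter names the diagnosis.

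   The conflict is sharpest in the second branch. A written diagnosis leaves the programme for findings where harm from silence is hardest to argue.

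3. **Other text on sharing.** Section 3.7 encourages the participant to share. Waiver condition 2 also speaks of encouraging adolescents to involve the trusted adult. Section 3.7.2 has staff suggest contact after a positive HIV test, although Section 7.6 lists HIV among conditions that may trigger the message. Section 7.6 gives a hub participant with nothing serious found their own letter and encourages them to share it. Read together, sharing is voluntary when nothing is found and automatic when something is.

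4. **Does nomination close the gap?** Under Section 7.5 the adolescent names an adult to be contacted should it become necessary, after the role is explained. The protocol does not say that this is permission to send diagnoses, or that any diagnosis counts as necessary. It expects the nominee often to be a parent, guardian or other relative. Yet condition 1 rests on the worry that participants will not be open "if they worry that their guardians will ask questions and will sanction them for being open".

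5. **The fallback.** If the adult does not respond about a more serious condition, Section 7.6 allows contact with the parent or guardian by telephone or home visit, after consulting the adolescent and staff. This is not limited to school recruits.

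6. **Reporting duties.** Section 3.7.2, on psychosocial issues, states a legal duty to report abuse of those under 18. It also has referral decisions taken in consultation with nominated trusted adults. Section 7.6 sends cases of rape or sexual abuse to the social development offices. The assurance mentions none of these.

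**The case against.** The strongest reply is that the recipient is not an arbitrary third party. The adolescent chooses the adult and need not choose a parent. Staff explain the role, verify the person when necessary before confidential information is shared, and revisit an unsuitable choice. Section 7.5 thus foresees sharing with this adult, and condition 2 relies on involving them. This stands, and it reduces the seriousness of the conflict. It does not remove it, because agreeing to be helped by a chosen adult is not stated to be agreement to a letter for each diagnosis.

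It can also be said that the more serious branch sends no diagnosis. That is correct for the message, though the message tells the adult there is a health matter to discuss. It does not help the letter branch.

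The encouragement in Section 3.7 describes what participants are asked to do and does not say that staff will refrain from contact. That is fair, so it is weaker evidence than the HIV text.

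Finally, the consent forms were not available for review, and they may describe contact with the trusted adult. If they do, participants may be better informed than the protocol suggests, but condition 3 would still need to match.

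**Conclusion.** The contradiction between waiver condition 3 and Section 7.6 holds on the wording of the protocol, for hub participants aged 16-17 with a condition diagnosed under Section 7.6. It should be corrected before the assurance is given at the hubs. This rests on reading participants' information as including screening results, and on the protocol text alone.

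Three stronger readings are tempting and are not supported:

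- *That the whole case for the waiver fails.* Only condition 3 as worded is contradicted. Condition 2 depends on the trusted adult, and condition 1 concerns guardians, whom the adolescent need not nominate. Since the conditions are to be met together, the argument is weakened, not defeated.
- *That every positive finding is disclosed.* Section 7.6 concerns diagnosed conditions, both lists are examples, and the final classification is left to Phase 1. STIs appear in neither list.
- *That the primary outcome is distorted by under-reporting.* Nothing in the protocol gives a direction or size for this, and a smaller denominator does not by itself bias a proportion.

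Nor can the number of adolescents affected be counted. The hub share of the 1000 Y-Check 2 participants is not fixed, and the 30% in Section 6.2 is an illustrative rate of screening positive, not of diagnoses that trigger Section 7.6.

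**What to change.** Reconcile Section 3.7 (community recruitment), Section 3.7.2 (psychosocial issues and HIV testing), Section 7.5 (trusted adult and waiver conditions) and Section 7.6 (both branches and the text on sexual abuse), so that hub participants hear before consent what will actually be sent, and to whom. Specifically:

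- State whether nominating a trusted adult is permission to disclose diagnoses or whether agreement is asked and recorded before a message or letter goes out.
- Name the mandatory-reporting exceptions within the assurance.
- Say whether the parent or guardian fallback in Section 7.6 applies to hub participants.
- Restate waiver condition 3 to agree with the chosen rule, and align the consent text.

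The cost is wording, plus one recorded item if agreement is to be asked. Section 8.4 requires approval of the amendment by the ethics bodies. If agreement is required, fewer adults may be informed, which could reduce support for completing referrals. If nomination is declared to be permission, some adolescents may be more reluctant to nominate or attend.

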# 7.6 Information sharing and disclosure

The protocol for sharing the results of the screening tests will vary according to the perceived seriousness of the condition and the age of the participant. The conditions that will be considered more or less serious or seriously stigmatized will be decided in collaboration with adolescents and stakeholders during Phase 1. More serious or seriously stigmatised conditions may include HIV, drug use, alcohol abuse, experiencing violence, suspected epilepsy, and serious musculoskeletal disorders Less serious or seriously stigmatised conditions may include anaemia, overweight, underweight, prehypertension, hypertension, myopia or a hearing disorder.

If the adolescent is diagnosed with a condition that is considered to be more serious and/or more seriously stigmatized, the adolescent's trusted adult (Y-Check 2 community hub) or the parent/guardian (Y-Check 1 and Y-Check 2 school-recruited) will be sent a message as soon as possible indicating that they should make an appointment with the Y-Check nurse/counsellor to discuss the adolescent's health. The nurse or counsellor would then meet with the adolescent and the adult/parent(s) together and would explain the condition or suspected condition and what is being recommended. They will ask for the adult/parent's support to manage the condition and answer any questions and give advice/support as needed. If the adult/parent does not take up the offer of an appointment, the study team will consult with the adolescent, and school, health or social care staff before deciding on next steps. Potential action would include contacting the parent/guardian by phone or through a home visit, and in emergency situations referring the young person to health/social services without the support of the parent/guardian.

If the adolescent is diagnosed with a condition that is considered to be less serious and/or less seriously stigmatized, the trusted adult (Y-Check 2 community hub) or the parent/guardian (Y-Check 1 and Y-Check 2 school-recruited) will be sent a letter indicating the diagnosis and the recommended treatment/action. Trusted adults or parents/guardians will be encouraged to support their adolescent through their treatment/care. The letter will also offer a way for the adult/parent to get an appointment with their adolescent so that they can ask any questions and receive advice/support as needed. If the adolescent needs their adult to accompany them to a referral appointment, then the Y-Check team would attempt to contact the adult by telephone or through a home visit. Otherwise, there will be no follow-up if the adult/parent does not take up the offer of an appointment.

If the adolescent is generally well then the adolescent will receive a one-page summary telling them what has been checked for and that nothing serious has been found. They will be encouraged to continue good health-related behaviours. They will be told about health and well-being services available at the school, the health facility and in the community. For Y-Check 1 and Y-Check 2 (school-recruited), the letter will be sent from the school to the parents. For Y-Check 2 (community-hub), the adolescent will receive the letter and will be encouraged to share with their trusted adult(s).

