#### 3.7.2 Screening tests and treatment/referral protocols

Screening tests and detailed treatment/referral protocols will be developed and implemented in line with national guidelines and best practice. As the screening of adolescents in Zimbabwe for many of the conditions listed below has not been implemented before, identifying locally accessible care pathways will involve working with existing services and potentially developing novel opportunities and pathways to address current gaps in service provision. During Phase 1 we will form a working group comprised of study investigators, health and social care, and disability stakeholders to decide on the final screening and referral strategies. Draft protocols are described here and in **Appendix 1**.

Psychosocial issues and alcohol, tobacco and substance use

Participants will respond to questions about their home, school/work, social activities, and exposure to violence and other risky situations using questions adapted from multi-domain psychosocial screening tools such as HEEADDSSS (Home, Education and Employment, Eating, peer activities, Drugs, Sexuality, Suicide/Depression, Safety and Security, Screens and Strengths) and other validated substance abuse questionnaires such as CRAFFT and Alcohol, Smoking and Substance Involvement Screening Test - Youth (ASSIST-Y)

Adolescents who are identified as high-risk including those who report experiencing or perpetrating violence, addiction to drugs or alcohol, or being suicidal will be referred to health, social and/or police services. The Y-Check team have a legal obligation to report certain findings such as domestic violence/abuse of children (<18 years of age) to the relevant authorities (e.g. the relevant department of the police, and the social welfare department for domestic violence or abuse). Decisions around referral will take place in consultation with school staff, parents/guardians and/or trusted adults who have been nominated by older adolescents (see section 7.6).

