# **Appendix 1: Conditions with correct management and subsequent outcomes**

Condition/risk behaviour	Screening tool	Primary Outcome: Appropriate on the spot care or complete appropriate referral		Secondary clinical or behavioural outcomes
		Appropriate on the spot care	Complete appropriate referral	
Psychosocial issues (home environment, education/employment, violence etc.)	Questions from HEEADSSS 	Counselling +/- referral	Attend first meeting with social services	Severity of psychosocial issue
Alcohol, tobacco and substance use	ASSIST-Y 	Brief intervention +/- referral	Attend first meeting with counsellor	Alcohol use Tobacco use Substance use
Common mental health disorders	Shona symptom questionnaire (SSQ) 	Counselling +/- referral to Youth Friendship Bench if SSQ score >=8. If 'red flag' refer to nearest health facility.	Attend first meeting of Youth Friendship Bench	Severity of symptoms
Low levels of physical activity	Questions from HEEADSSS 	Counselling and advice		Level of physical activity
Poor diet	Questions from HEEADSSS 	Counselling and advice +/- referral	Attended first appointment at food supplementation services	Frequency of fruit and vegetable intake Frequency of sugary beverage intake
Underweight	MUAC, BMI, BVI	Counselling and advice +/- referral	Attended first appointment at food supplementation services	MUAC/BMI/BVI
Overweight	MUAC, BMI, BVI	Counselling and advice		MUAC/BMI/BVI
Anaemia	Hemocue	Iron and folic-acid supplementation (3 months supply) if anaemic. If severely anaemic (<8g/dl) refer to health facility.	Attended first appointment at health facility.	Anaemia

Poor oral health	Questions on oral health.  Visual inspection.	Advice, gift of toothpaste and toothbrush, fluoride varnish application +/- SDF application +/- referral	Attended first appointment at dentist	Reported pain or swelling. Frequency of tooth brushing
Uncircumcised	Question on circumcision status. Visual inspection.	Referral for VMMC (males only)	Attended first VMMC referral appointment.	Circumcised
Unprotected sex	Question (s) on sexual activity	Risk reduction counselling, Provision of condoms, Provision of modern contraceptives (emergency contraception, depot injections, oral contraceptive pill) (females only)  PrEP (females only)		Frequency of unprotected sex  Modern contraceptive use (females)  PrEP use (females)

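### Section 7.6 states no exception to parent/guardian contact when that adult is the suspected source of violence, and the protocol does not place the required report before that contact

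*Protocol*

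**What the plan says.** The check-up asks directly about violence. In Section 3.7.2, "Participants will respond to questions about their home, school/work, social activities, and exposure to violence and other risky situations", and Appendix 1 has a row for "Psychosocial issues (home environment, education/employment, violence etc".

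Section 7.6 divides findings by seriousness and stigma, with the final division left to Phase 1. Its provisional wording is: "More serious or seriously stigmatised conditions may include HIV, drug use, alcohol abuse, experiencing violence". For findings in that group, "the parent/guardian (Y-Check 1 and Y-Check 2 school-recruited) will be sent a message as soon as possible", asking for an appointment on a health matter concerning the young person. At that appointment a member of the clinical team "would then meet with the adolescent and the adult/parent(s) together and would explain the condition or suspected condition". Staff also seek the parent's support in managing it.

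Reporting duties stand elsewhere. Section 3.7.2 has adolescents who report violence referred to health, social or police services, and recognises a "legal obligation to report certain findings such as domestic violence/abuse of children (<18 years of age". It adds that referral decisions are taken "in consultation with school staff, parents/guardians and/or trusted adults who have been nominated by older adolescents", and points to 7.6. A separate paragraph of 7.6 sends rape and sexual abuse to the District Social Development Offices under Ministry reporting guidelines.

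**The concern.** A programme that asks children about home and violence must expect some to disclose harm by a parent or guardian. For a school-recruited child, the written rule then leads to that same adult. Staff who followed 7.6 literally could summon a suspected perpetrator before any report was made, and then explain the finding to that adult with the child in the room.

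The protocol already accepts that family knowledge can hurt the adolescent. Section 7.4 names the consequences of a parent learning of a drug or alcohol problem, and rejection by family after a positive result. Section 7.5, in arguing for the parental-consent waiver at community hubs, says that guardians may punish openness. An exception in 7.6 would apply the same reasoning where the parent is the suspected cause of the harm.

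**Working it through.** No arithmetic applies. The check sets the relevant texts side by side.

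1. **Is the case foreseeable?** Yes. Section 3.7.2 asks about home and exposure to violence, and Appendix 1 lists violence under a screened issue.
2. **Which disclosure rule governs?** Section 3.7.2 refers to 7.6, and 7.6 names experience of violence as an example in its more serious group. The example is provisional.
3. **What does that rule do for a school recruit?** It sends a message to the parent or guardian as soon as possible, and then holds a joint meeting. The message asks for an appointment and is not stated to name the finding. The meeting explains it.
4. **When may staff depart from the rule?** Section 7.6 describes a departure only after the parent fails to take up the appointment. Staff then consult the adolescent and school, health or social care staff. They may phone or visit the parent or, in an emergency, refer without the parent's support. None of this depends on who is suspected.
5. **Is the report placed first?** Section 3.7.2 states the violence referral and the legal duty, and 7.6 states the sexual abuse referral. None is ordered relative to the parental contact. The wording in 3.7.2 on consultation allows a parent to be left out but does not require it.
6. **Does another section supply the exception?** Section 7.5 lets staff question whether a nominated trusted adult is suitable, but in the paragraph on hub registration (16-19 years). Section 7.4 promises family-communication procedures without committing them to this case. Section 4.1 provides for work with Child Protection Committees and 7.8 for monitoring of social harms; neither is stated to precede the first parental contact.

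Result: no stated exception for a suspected parent or guardian, and no statement that the report comes before contact with them.

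**Who is covered.** Section 3.7 delivers Y-Check 1 (10-14 years, 1000 planned) only in primary schools, so all of these children fall under the parent route, as does the school-recruited part of Y-Check 2. That is the group governed by the rule, not the number at risk. The documents give no figure for disclosures of violence by a parent.

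**The case against.** The strongest reply is that the text is openly unfinished. The list of serious conditions is provisional, 3.7.2 calls its protocols drafts to be settled by a working group that includes social care stakeholders, and family-communication procedures are still to come. On this view the gap is detail for an operating procedure. It stands in part, since Phase 1 could add the exception. But what Phase 1 is committed to is classifying conditions and developing general communication procedures. Meanwhile 7.6 states a positive rule whose literal application is unsafe in this case.

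Second, a violence-specific route exists. Referral is made at the nurse review (Section 3.7.3, Station 5), the joint meeting waits for an appointment, and a specific reporting rule may be read as overriding a general results-sharing rule. Sensible staff may well report first, and nothing in the protocol puts the meeting ahead of the report. The protocol simply does not settle the order.

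Third, the law and Ministry guidelines may fix the order. They are not shown, so this can be neither confirmed nor excluded.

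Fourth, a reader might count the letter route for less serious findings, under which the adult "will be sent a letter indicating the diagnosis and the recommended treatment/action", as a second unsafe path. The documents do not support that: the examples given for that group are physical conditions, and nothing suggests that violence will be moved there.

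**Conclusion.** The point holds in a narrow form and should be fixed; confidence is medium. As written, 7.6 routes a school recruit's disclosure of violence to the parent or guardian with no exception for a suspected perpetrator, and the protocol does not put the report first. The main exposure is the joint meeting.

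Two stronger readings should be avoided. A reader might infer that the protocol lacks a duty to report; it has one, in 3.7.2 and again in 7.6 for sexual abuse, but without a stated order. A reader might also infer that the first message reveals the disclosure; it is described only as a request for an appointment.

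The conclusion assumes that violence stays in the more serious group and that no procedure outside this document already supplies the exception. Its size cannot be quantified from the documents. It concerns participant safety and makes no claim about the study's estimates.

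**What to change.** Add to 7.6, with a cross-reference in 3.7.2: where a parent or guardian is the suspected source of violence or abuse, the message to that adult, the joint meeting with them and their consultation on referral are withheld until the case has been reported under 3.7.2 or the rape/sexual abuse paragraph of 7.6. Later family contact follows the advice of those authorities and the applicable guidelines. Contact with a non-offending parent is otherwise unchanged unless the authorities advise against it. The follow-up questions at the nurse review can be used to establish the suspected source before any message is sent.

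The cost is a short amendment and a matching operating procedure, using reporting routes already in the plan. Section 8.4 requires approval by the MRCZ, the LSHTM Ethics Committee and the BRTI IRB before implementation. The drawback is delayed involvement of that adult in some cases, including some where the suspicion proves wrong.
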